The quality of life as assessed by ANCOVA analysis of the KCCQ summary score for complete 2-year data showed an improvement of 7.8 ± 2.3 points for the device arm compared to decline of 12.1 ± 2.3 points for the control arm. Similarly, 6MWD outcomes showed a decline of 55 ± 10.8 points for the device arm vs decline of 93.5 ± 10.9 for the control arm. Adverse event rates were consistently low and strongly in favor of the device arm. Overall, the data concluded that at 36 months transcatheter mitral leaflet approximation with the MitraClip was safe, provided durable reduction in MR, reduced the rate of HF hospitalizations, and improved survival, QOL and functional capacity compared to GDMT alone.

Based on this clinical evidence clinical benefit of MitraClip System continues to demonstrate significant benefit to MR patients and is suitable for use in the study for safety and efficacy in the Russian population.

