5.3.2 Inclusion Criteria

5.3.2.1 General Inclusion Criteria

- Age 18 years or older.
- Symptomatic moderate-to-severe (3+) or severe MR (4+) chronic DMR or FMR determined by assessment of a qualifying transthoracic echocardiogram (TTE) obtained within 90 days or transesophageal echocardiogram (TEE) obtained within 180 days prior to subject registration.
 - LVEF \geq 30%
 - NYHA classification is class II, class III, or ambulatory class IV.
 - Subject is deemed difficult for mitral valve surgery due to either STS surgical mortality risk for mitral valve replacement of \geq 8% OR due to the presence of one of the following risk factors:
 - Porcelain aorta or mobile ascending aortic atheroma
 - Post-radiation mediastinum
 - Previous mediastinitis
 - Functional MR with LVEF $<$ 40%
 - Over 75 years old with LVEF $<$ 40%
 - Re-operation with patent grafts
 - Two or more prior cardiothoracic surgeries
 - Hepatic cirrhosis
 - Other surgical risk factor(s)
 - Mitral valve area \geq 4.0 cm².
 - The primary regurgitant jet is non-commisural, and in the opinion of the implanting investigator can successfully be treated by the MitraClip NT System. If a secondary jet exists, it must be considered clinically insignificant.

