Administer additional intravenous doses of antibiotics at approximately 6 and 12 hours (or per institutional guidelines) after the completion of the procedure.

Subjects will receive standard post-cardiac catheterization procedure care as judged appropriate by the Investigator.

Subject weight, blood pressure, heart rate and temperature must be obtained prior to subject discharge from the hospital.

At discharge, each subject implanted with a **MitraClip NT** device(s) must be provided an Implant Identification Card. An Implant Identification Card is included in the package with each **MitraClip NT** System. The subject must be instructed to keep this Implant Identification Card on their person at all times. The serial number of all implanted **MitraClip NT** device(s) must be recorded on the Implant Identification Card.

The Investigator must instruct all subjects who receive the **MitraClip NT** device of the need for prophylaxis for endocarditis, as recommended in the guidelines for the prevention and treatment of infective endocarditis. Subjects must be instructed to notify the Investigator or the subject's primary care physician in the event that a procedure recommended by this Guideline is planned, so that prophylactic antibiotics can be prescribed. Post- **MitraClip NT** procedure anticoagulation is recommended per the Investigator's discretion as follows:

1. Reinitiate warfarin, dabigatran or factor Xa inhibitor (if discontinued for the **MitraClip NT** procedure) at pre-procedure levels or as appropriate. If chronic oral anticoagulation is used, then aspirin and ticlopidene use are not recommended, but are allowed if otherwise indicated for other conditions.
2. If chronic oral anticoagulation is not used, it is strongly recommended that either daily ticlopidene and/or aspirin (81 mg) is administered for 6 months or longer. If aspirin is to be used, a dose of 325 mg acetylsalicylic acid (ASA) may be administered either pre- or immediately post- **MitraClip NT** procedure followed by 81 mg per day for 6 months or longer per Institutional standards and at the discretion of the Investigator.

Follow-up for All Subjects

Clinical follow-up will be performed at the following intervals for all enrolled subjects, regardless of whether a **MitraClip NT** device was successfully implanted:

Discharge post- **MitraClip NT procedure**

- 10 days follow-up office visit (this visit must be conducted even if subject is in hospital);
- 30 days.

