#### 1.3 Clinical Investigation Design

The MitraClip Russia trial is a prospective, single-center, single-arm clinical evaluation of the MitraClip System for the treatment of symptomatic chronic moderate-to-severe (3+) or severe (4+) Degenerative Mitral Regurgitation (DMR) or Functional Mitral Regurgitation (FMR) in Russia subjects deemed difficult for mitral valve surgery by the local site heart team. Follow-up of subjects enrolled in the MitraClip Russia study will occur at discharge, 10 days, and 30 days. Sixteen (16) subjects will be registered in this study.

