## Statistical Analysis Plan

- Number of hospitalizations and reason for hospitalization (i.e. heart failure, cardiovascular, non-cardiovascular) through follow up
- Major bleeding requiring transfusion through follow up
- Six Minute Walk Test (6MWT) distance at baseline, 10 days and 30 days
- Average doses of concomitant cardiac medications at baseline, procedure, 10 days and 30 days.
- New York Heart Association (NYHA) Class at baseline, 10 days, 30 days

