#### 2.2.1 Descriptive Statistics for Continuous Variables

For continuous variables such as age, results will be summarized with the numbers of observations, means, standard deviations, and, if specified in the table mockups, with quartiles, minimums, and maximums.

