#### 2.3.2 Descriptive Endpoints

The analyses for the descriptive endpoints will be performed using the methods described in Section 2.2 for ATP populations.

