## Statistical Analysis Plan

### 2.7 Handling of Missing Data

All analyses will be based on available data with missing data excluded. Any unused or spurious data will be noted as appropriate in the final report.

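### SAP 2.7 does not separate a living subject who cannot walk from a missing 6MWT, so unless the CRF records 0 m such a subject leaves the follow-up mean and inflates it

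*SAP*

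**What the plan says.** SAP 1.4.2 and Protocol 4.2 list the endpoint in the same terms: "Six Minute Walk Test (6MWT) distance at baseline, 10 days and 30 days". SAP 2.3.2 sets the method: "The analyses for the descriptive endpoints will be performed using the methods described in Section 2.2 for ATP populations". For a continuous variable, SAP 2.2.1 says that "results will be summarized with the numbers of observations, means, standard deviations", with quartiles and range only where the table mockups ask for them. Protocol 8.3 adds a 95% confidence interval for the mean, assuming approximate normality.

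SAP 2.7 gives one rule for every endpoint: "All analyses will be based on available data with missing data excluded". Its second sentence says that unused or spurious data will be noted in the final report as appropriate.

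The primary endpoint has its own rule for known bad outcomes: death or mitral valve surgery before discharge counts as failure (SAP 1.4.1 and 2.3.1). The 6MWT has no counterpart. Neither document assigns a value, a reason code or a sensitivity summary to a test not done because the subject could not walk.

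**The concern.** A subject who comes to the visit but cannot walk because of heart failure, a stroke or a procedural complication has a known functional result. If the distance field is left blank, SAP 2.7 treats that result as unknown and removes it. What is lost is the poorest function in the sample, so the loss can only raise the follow-up mean.

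Baseline is not affected in the same way. Entry requires that "NYHA classification is class II, class III, or ambulatory class IV", so the same subject will normally have a baseline distance that stays in the baseline mean. Anyone comparing the two means then compares different sets of people.

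The situation is foreseeable. Protocol Table 5 lists stroke, worsening heart failure and prolonged ventilation among the anticipated events. Protocol 6.1 says of day 10 that "this visit must be conducted even if subject is in hospital", and the schedule in Protocol 6.2 places a 6MWT at that visit. With 16 subjects, one or two such cases visibly move a mean. In a single-arm study without hypothesis tests, these summaries are the evidence.

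**Working it through.** The documents give no expected 6MWT mean, SD or rate of inability, so there is no figure of the plan's own to reproduce. What follows is an illustration.

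**Inputs**
- N = 16, from SAP 1.3: "Sixteen (16) subjects will be registered in this study". All 16 are taken as alive and attending, and everyone able to walk is tested.
- k = number physically unable to walk (assumed).
- M = mean distance of the other 16 − k subjects, assumed to be 200 to 350 m.

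**Effect on the follow-up mean**
- Available-case mean under SAP 2.7, with a blank field: M, on n = 16 − k.
- Mean with 0 m for those unable to walk: M × (16 − k)/16, on n = 16.
- Difference: M − M × (16 − k)/16 = M × k/16.

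| M (m) | k = 1 | k = 2 |
|---|---|---|
| 200 | 12.5 | 25.0 |
| 250 | 15.6 | 31.2 |
| 300 | 18.8 | 37.5 |
| 350 | 21.9 | 43.8 |

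Relative to the mean that counts all 16, the overstatement is k/(16 − k): 1/15 = 6.7% for one subject and 2/14 = 14.3% for two.

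**Without assigning 0 m.** A simulation of 16 distances (assumed mean 280 m, SD 80 to 120 m) with the lowest value removed raised the expected mean by about 9 to 14 m. With the two lowest removed, the rise was about 17 to 26 m. The direction does not depend on the choice of zero.

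**Baseline against follow-up.** Suppose 14 subjects walk 300 m at both times, and two walk 150 m at baseline and cannot walk at follow-up.
- Baseline mean, n = 16: (14 × 300 + 2 × 150)/16 = 281.25 m.
- Follow-up mean under SAP 2.7, n = 14: 300 m, an apparent gain of 18.75 m.
- Follow-up mean with 0 m, n = 16: 14 × 300/16 = 262.5 m, a loss of 18.75 m.
- Same 14 subjects at both times: 300 m and 300 m, no change.

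Matching the baseline to those tested removes the false gain but does not show the loss. The score of 0 m and the count unable to walk are needed for that.

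**The case against.** The strongest objection is that the key step is inferred. SAP 2.7 excludes missing data; it does not say that inability to walk is missing. If the CRF has sites enter 0 m, the value is available and no bias arises. This stands, and it makes the point conditional. But neither document says that 0 m is entered.

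Four stronger readings are tempting, and the documents do not support them.

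- *The reported 6MWT mean will be biased.* It will be only if at least one living, attending subject cannot walk and no 0 m is entered. Being in hospital on day 10 is not the same as being unable to walk. Protocol 1.2 gives a typical recovery of two to three days, and Protocol 2.2.4 reports average stays below 3 and below 4 days in the earlier randomized trial and high-risk registry.
- *The report would hide these subjects.* SAP 2.2.1 requires the number of observations, so n = 14 against n = 16 would show. NYHA class, the modified Rankin scale and adverse event reports also capture poor status. What is not assured is the reason for the missing test.
- *The bias is as large as a treatment effect.* Protocol 2.2.4 says of an earlier randomized trial: "Similarly, 6MWD outcomes showed a decline of 55", against 93.5 in the control arm, a difference of 38.5. That is a between-arm difference presented with two-year data and printed in points. The value of 37.5 m above comes close only because k = 2 and M = 300 m were chosen. It is no yardstick for a single-arm mean at 10 or 30 days.
- *The plan misreports change from baseline.* Change in 6MWT is not a defined endpoint. The false gain arises when a reader subtracts two means with different n.

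Scale also matters. With an assumed SD of 80 to 120 m, the standard error at n = 16 is 80/4 to 120/4 = 20 to 30 m. The 95% half-width is about 43 to 64 m (t = 2.13), so the effect of one non-walker lies inside it. That limits the importance of the point, but bias in a known direction is not excused by imprecision.

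**Conclusion.** The point holds in conditional form. SAP 2.7 is a stated rule that, applied as written to a blank 6MWT field, drops the worst functional results at day 10 or day 30 and keeps their baseline values. Relative to scoring 0 m, the follow-up mean is then too high by M × k/16: 12.5 to 22 m for one of 16 and 25 to 44 m for two, at an assumed M of 200 to 350 m. The effect is nil if every subject walks or if the CRF records 0 m.

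The 6MWT is descriptive and Protocol 8.3 plans no hypothesis tests, so no error rate and no part of the primary endpoint is affected. The change should still be made before the analysis, because the direction is known and the correction is cheap.

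**What to change.** 1. On the CRF, record the reason for every 6MWT not done: physically unable to walk, withheld on medical grounds, death, or other/missed visit.
2. In SAP 2.7, state that a test not done because the subject is physically unable to walk is not missing and is scored 0 m. Show the available-case mean alongside as a sensitivity summary.
3. State that deaths and tests withheld on medical grounds are counted separately and are not scored 0 m under this rule.
4. Report the number of subjects in each reason category at each visit.
5. Give the median and quartiles with the mean. The mockups may already ask for quartiles; the SAP text should require them here.
6. Beside each follow-up summary, show baseline values for the same subjects who contribute at that visit.

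The cost is a few sentences in the SAP, one field on the paper CRF and some extra table rows. The downside is a larger SD and a slightly less favourable mean. Zeros also strain the normality assumption behind the confidence interval in Protocol 8.3, which is why the median and the counts belong beside it. A worst-rank rule would also be defensible; what matters is that one rule is fixed before the analysis.

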### 3.0 DOCUMENTATION AND OTHER CONSIDERATIONS

All analyses will be performed using SAS® for Windows, version 9.3 or higher.

### 4.0 ACRONYMS AND ABBREVIATIONS

Acronym or Abbreviation	Complete Phrase or Definition
6MWT	6-Minute Walk Test
ATP	Attempted Procedure Population
CCU	Critical Care Unit
CDS	Clip Delivery System
CI	Cardiac Index
CIP	Clinical Investigation Plan
CO	Cardiac Output
DMR	Degenerative Mitral Regurgitation
FMR	Functional Mitral Regurgitation
FSV	Forward Stroke Volume
HRR	High Risk Registry
ICU	Intensive Care Unit
IFU	Instructions For Use
LVEDD	Left Ventricular End Diastolic Dimension
LVEF	Left Ventricular Ejection Fraction
LVESD	Left Ventricular End Systolic Dimension
LVESV	Left Ventricular End Systolic Volume
MI	Myocardial Infarction
MR	Mitral Regurgitation
MVA	Mitral Valve Area
MVG	Mitral Valve Pressure Gradient
NYHA	New York Heart Association
PACU	Post-Anesthesia Care unit
RF	Regurgitation Fraction

*This confidential document is the property of Abbott and shall not be reproduced, distributed, disclosed or used without the express written consent of Abbott.*

## Statistical Analysis Plan

Acronym or Abbreviation	Complete Phrase or Definition
RV	Regurgitation Volume
RVSP	Right Ventricular Systolic Pressure
SAE	Serious Adverse Event
SAP	Statistical Analysis Plan
TEE	Transesophageal Echocardiogram

